9.0 Study Design / Methods

- **Study design:** The study will use a 2×2 crossover design. Participants will be randomly assigned to either the treatment or control condition for the first month, followed by a 2-week washout period and then crossover to the other condition. For both conditions, participants will be instructed to wear TheraBracelet on the affected wrist every day for at least 8 hours/day during their daily activity over a month. The device will apply wrist vibration at 60% of the sensory threshold (imperceptible) for the treatment condition, and no vibration for the control condition. The control condition is needed to assess safety of TheraBracelet in comparison to that of simply wearing a wristband, thereby accounting for any worsening of symptoms that may occur as a natural course after stroke. Half the participants will start with the treatment and half with the control (balanced).
- **Schedule:** One person's participation will be 2.5 month long (= 1 month for one condition, 2 week washout period, 1 month for another condition). For each condition, participants will come to the laboratory once a week for evaluation for a total of 5 times: The 1st visit will entail the baseline evaluation followed by an introduction to using the device. Subsequent visits will be for evaluation after using the device each week. A follow-up assessment will be administered 4-16 weeks after the 10th session if any safety measure has worsened as defined as an adverse event by the 10th visit compared to the 1st visit. The follow-up assessment will evaluate only the measure that has worsened.
- Evaluation will include feasibility, safety, and durability, as detailed below.

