detectable change (MDC) (also known as the smallest real difference, Chen et al 2009). Hand dexterity will be determined to have deteriorated if the Nine Hole Peg or Box and Block Test score worsens by more than 20% (approximately 2 standard deviation of the population data) and MDC (Chen et al 2009). Hand strength and dexterity measurement will be performed three times during the baseline testing. Upper limb pain will be assessed using the visual analog pain rating scale (0 to 10). Upper limb pain will be determined to have increased if the pain level indicated on the visual analog pain rating scale increases by more than 2. Spasticity will be show assessed using the Modified Ashworth Scale (MAS). Spasticity will be determined to have worsened if MAS increases by more than 1 point (equivalent to the effect size of botulinum toxin A). Wrist skin irritation and increased swelling, if there is any, will be noted. Rigorous safety criteria will be used in which adverse events will be noted if any of the measures (hand sensation, strength, dexterity, pain, spasticity, skin irritation, swelling) worsens at any of the four evaluation times compared to the baseline. The co-investigator and study neurologist, [name], will meet with each participant in person or via teleconference to interview the participant regarding safety related to wearing the device.

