- **Durability:** The durability of TheraBracelet's instant effect will be examined by assessing TheraBracelet's instant effect in each weekly evaluation and comparing them across. The instant effect will be quantified as increase in the hand touch sensation (Monofilament Test) dexterity scores (Nine Hole Peg and Box and Block Tests) with vibration turned on compared to off, with the 'on' and 'off' tested in a random order, blinded, within a single evaluation session. If TheraBracelet's instant effect is seen for all evaluation times, it will support durability (i.e. desensitization to vibration does not occur). In addition, the impact of TheraBracelet on stroke survivors' self-reported abilities for activities of daily living and quality of life will be assessed. Specifically, the Stroke Impact Scale, SIS (sections of the hand, activities of daily living, and recovery), and Stroke Specific Quality of Life, SS-QoL (sections of the self-care and upper extremity function), will be obtained at weekly evaluations and compared between the two conditions. The Nine Hole Peg and Box and Block Tests will be videoed to ensure the exact start and stop time are recorded. This video will not include the participant's face in order to maintain confidentiality.
- **Protection against risk:** For fatigue, frequent sufficient breaks will be provided to participants. As for potential skin irritation due to wearing the wristband, the wristband tightness may be adjusted with a new wristband to maximize participant comfort. Participants will be notified if we learn anything that might make them change their mind about participating in the study. Potential risks of deterioration of hand sensation, strength, and dexterity, increased upper limb pain level and spasticity level, and/or wrist skin irritation will be monitored every week during the weekly evaluation when participants come to the laboratory. In fact, these events are the outcome measures of safety for the primary aim of the study. Participants will be informed that they can drop out of the study any time without penalty.

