10.0 Data Management

- **Confidentiality protection:** The data from test results will be de-identified once it has been collected and before it is stored. This means individual results would not be able to be linked to the participant by others who review the results of this research. The linkage between participant codes and identities as well as all other identifiable

information including consent forms will be stored in a locked room and be accessible only to the study personnel.

- Statistical analysis: For Primary Aim of feasibility and safety, we will compare rates of compliance and device-related adverse events between the treatment and control conditions using the test of non-inferiority. For safety, we will analyze the data using the “intent to treat” paradigm. The meaningful difference in adverse events to detect between the treatment and control is 20% for the following reason. For a regulatory approval, a safety level similar to a comparable FDA-approved device is desired. One such device, with availability of safety data, is a Bioness electrical stimulator for foot drop: It has a 21% higher likelihood for adverse events compared to a standard ankle foot orthosis (Kluding et al. 2013). Based on power analysis below, we will be sufficiently powered to statistically discern different rates of adverse events if more than 3 out of 24 participants experience adverse events in the treatment vs. control condition. In other words, if 3 or less participants out of 24 experience adverse events in the treatment vs. control condition, we will deem TheraBracelet safe for the purpose of an FDA approval. We will verify that there is no order effect using exact binomial tests.
- For feasibility, compliance will be defined as participants’ use of the device for at least half the prescribed time. The reason is that 4 hours/day is still a substantial use of this assistive device in daily living, and will provide sufficiently useful information about feasibility of TheraBracelet. Similarly with the analysis for safety, if 3 or less participants out of 24 are incompliant in the treatment vs. control, we will conclude that TheraBracelet is as feasible as wearing a non-vibrating wristband. The cumulative hours of device usage will also be examined for both conditions to inform the general usage trend.

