- For the secondary outcome of durability of TheraBracelet’s instant effect, the hypothesis will be tested using repeated measures ANOVA for each hand function measure, with factors of vibration (on/off), condition (treatment/control), evaluation time (1-5), and their interactions. A significant main effect of vibration, with improved hand function with vibration on vs. off, with non-significant interactions of vibration×evaluation time and vibration×condition, would indicate durability over a month. In contrast, a lesser extent or abolishment of the instant effect toward the later evaluations or for the treatment condition, with significant interactions of vibration×evaluation time or vibration×condition, would indicate desensitization. In that case, the time point at which the instant effect wanes will be examined using Tukey type posthoc pairwise comparisons.
- A possibility exists that instant enhancement of hand function with TheraBracelet may trigger more use of the affected hand in daily living, which, when accumulated over time, might lead to improvement of the innate hand function (without vibration). This is analogous to cane users who may walk more with canes than without, and thus build greater lower limb abilities over time. Thus, change in the innate hand function will be examined. A significant effect of condition×evaluation time, with greater improvement of the innate hand function for the treatment vs. control, will suggest a therapeutic effect of TheraBracelet for secondary investigation.
- Impact of TheraBracelet on activities of daily living and quality of life will be assessed using repeated measures ANOVA for the SIS and SS-QoL, with the main effect of condition.

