- Power analysis: The sample size for the primary outcome of safety was determined for testing hypothesis of non-inferiority using a 2×2 crossover at 80% power and 5% significance level. A sample size of 24 (12 in each condition at randomization) provides sufficient power to conclude non-inferiority within a difference in adverse events of 20% between the discordant pairs (those who are safe with control but unsafe with treatment vs. those with the opposite), assuming a total of 10% discordance rate (proportion of participants with different responses for the two conditions) and a 90% safe rate for the control. That is, we will be powered to statistically conclude non-inferiority (hence safety) if 3 or less out of 24 participants have adverse events in treatment vs. control. For the Secondary Aim involving repeated measures ANOVA, with the effect size of $f=0.25$ for the Box and Block from our previous study, (Seo et al., 2014) a sample size of 19 is needed assuming a conservative correlation of 0.3 across evaluation times, for 80% power and 5% significance level. Thus, we will aim to obtain data from 24 participants. Considering that some may be found ineligible after enrollment, a total of 30 recruitment is proposed.
- Data sharing: Only de-identified coded data will be reported and/or shared with the public in publications, in ClinicalTrials.gov, or upon written request.

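### A non-significant exact binomial test cannot verify that there is no order effect with 24 participants; separately, the SIS/SS-QoL condition comparison should name a period term (minor)

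*Combined protocol and SAP*

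**What the plan says.** The design is a 2×2 crossover with balanced allocation to sequence and a two-week washout (combined protocol and SAP, section 9.0, Study design).

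- **Order check.** Section 10.0, Statistical analysis, in the bullet on safety: "We will verify that there is no order effect using exact binomial tests". The plan does not give the counts to be compared, the null proportion, the level, the sidedness or what follows from a positive result. It does not say whether order means period, sequence or carry-over.
- **Planning values.** Section 10.0, Power analysis, sizes the trial at 24, "assuming a total of 10% discordance rate" and a 90% safe rate on control, with a 20% margin.
- **Event definition.** Section 9.0, Safety, counts an event if any listed measure "worsens at any of the four evaluation times compared to the baseline".
- **Primary decision.** This is stated as a count: "if 3 or less participants out of 24 experience adverse events in the treatment vs. control condition, we will deem TheraBracelet safe". The compliance rule follows the same pattern. Neither refers to the order check.
- **SIS and SS-QoL.** These scales "will be obtained at weekly evaluations and compared between the two conditions" (section 9.0, Durability). Their impact analysis "will be assessed using repeated measures ANOVA for the SIS and SS-QoL, with the main effect of condition" (section 10.0). The durability model in the same section lists its factors as vibration, condition and evaluation time (1–5). Evaluation time there is the visit within a condition, so neither model names crossover period.

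**The concern.** Verifying that there is no effect by means of a significance test treats failure to reject as evidence of absence. That is unsound at any sample size. Here few discordant participants are expected, so a non-significant result would be likely even if a real order effect existed. The report could then state that order effects had been ruled out when the data had little capacity to show them.

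The SIS/SS-QoL point is about efficiency. These are self-reported scales collected over about 2.5 months, so scores may shift between the first and second month whatever the condition. A crossover analysis without period leaves that shift in the error of the condition comparison, although the data needed to remove it are already collected.

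**Working it through.** **Plan's own figure.** The plan gives no figure for the order test, only N = 24 for paired non-inferiority. With discordance 0.10, margin 0.20 and true difference 0, the Wald formula N = (z_α + z_β)² × 0.10 / 0.20² gives (1.645 + 0.842)² × 2.5 = 15.5, so 16, at one-sided 5%. At one-sided 2.5% it gives 20. A score-type test at one-sided 5% gives 26 asymptotically, and exact enumeration gives 82.4% power at N = 24. So 24 is consistent with a one-sided 5% score-type test, and the 10% discordance is taken as the planning value.

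**Order test, assumed reading.** Let D be the number of participants with an event in exactly one period, and test whether half of these events fall in period 1.

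1. Smallest attainable p-value with all D in one direction: two-sided 2 × 0.5^D, which is 0.0625 at D = 5 and 0.031 at D = 6; one-sided 0.5^D, which is 0.0625 at D = 4 and 0.031 at D = 5. Rejection needs D ≥ 6 two-sided or D ≥ 5 one-sided.
2. At 10% discordance D ~ Binomial(24, 0.10), with mean 2.4. P(D ≥ 6) = 2.8% and P(D ≥ 5) = 8.5%. These are ceilings, reached only if every discordant participant falls in the same direction.
3. The period difference in event rates is the difference between the two discordant proportions, so it cannot exceed their sum. At 10% discordance the order effect is therefore at most 10 points, and the ceilings apply to that case.
4. Larger order effects require more discordance. Two-sided power, N = 24:

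| Period difference | Independent periods, 10% in the lower period | All discordance in one direction |
|---|---|---|
| 20 points | 30% v 10%: discordance 0.27 + 0.07 = 0.34, share 0.79; power 26% | discordance 0.20; power 34% |
| 30 points | 40% v 10%: discordance 0.36 + 0.06 = 0.42, share 0.86; power 55% | discordance 0.30; power 77% |

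5. Alternative reading: participants with any event, split by sequence. Event rates of 10% per condition with 10% discordance imply 10% + 10% − 5% = 15% with any event. P(at least 6 of 24) = 13.9%, again a ceiling.
6. What an interval would show (exact 95%, share of discordant events in period 1): 1 of 2 gives 1% to 99%; 3 of 3 gives 29% to 100%.

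**SIS/SS-QoL condition comparison.** The plan states no power for this, so the following is illustrative. Assume a condition effect of 0.60 SD of the within-person difference, 12 completers per sequence, two-sided 5%. A period shift of s SD moves the treatment-minus-control difference by +s in one sequence and −s in the other. The mean is unchanged, and the error variance is multiplied by about 1 + s². The noncentrality parameter is 0.60 × √24 / √(1 + s²), with 23 df.

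| Shift s | Power without period (noncentral t / simulation) |
|---|---|
| 0 | 80.4% / 80.4% |
| 0.2 | 78.8% / 79.1% |
| 0.25 | 78.0% / 78.5% |
| 0.5 | 71.2% / 72.9% |
| 1.0 | 51.3% / 50.3% |

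With period in the model (22 df) power is 80.2% at every shift. Without it the test is conservative: simulated type I error is about 3% at 0.5 SD and 0.6% at 1.0 SD.

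If completers are unequal, the fraction of the shift entering the estimate is (n₁ − n₂)/(n₁ + n₂). An assumed 12 v 11 gives 1/23 = 4%. An assumed 12 v 10 gives 2/22 = 9%, or about 0.05 SD for a 0.5 SD shift.

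**The case against.** The case against has real force.

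- **The 2.8% belongs to a small effect.** Fixing discordance at 10% fixes the order effect at 10 points or less, half the difference the plan calls meaningful. A real order effect would raise discordance, and so could the broad any-measure, any-visit event definition without an order effect. A reader might infer that the test could never detect anything. The documents do not support that: at 20 to 30 points it has appreciable, though inadequate, power.
- **The contrast is assumed.** The plan does not define it, and the 10% is an adverse-event value. There is no discordance rate for compliance, so no compliance figure can be computed. The sentence stands in the safety bullet, and extending it to compliance is an inference.
- **Nothing primary rests on it.** A reader might infer that the safety or compliance conclusion is undermined. It is not: both rules are counts that do not use the order test, and with balanced sequences an additive period effect does not bias the treatment–control difference.
- **SIS/SS-QoL.** The plan may be naming the effect of interest and not the whole model; evaluation time is not named there either. Nothing in the documents suggests a shift as large as 0.5 SD, and below about 0.25 SD the loss is immaterial. A reader might infer bias or extra false positives, but with 12 per sequence there is no bias from an additive shift and the test is conservative. Carry-over is made plausible by section 10.0's own remark about lasting gains in innate hand function, and a period term does not remove it.

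What survives is the word verify, which claims more than the test can give, and an inexpensive term that the plan does not name.

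**Conclusion.** The point holds in limited form and is minor. A non-significant exact binomial test with 24 participants cannot establish absence of an order effect. On the assumed sign-test reading, the chance of rejection is at most 2.8% two-sided (8.5% one-sided) at the plan's 10% discordance, where the order effect is at most 10 points. It is about 26–34% at 20 points and 55–77% at 30 points, so the test is underpowered but not empty. The consequence is an unsupported sentence in the report; the primary decision rules are unaffected.

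For SIS and SS-QoL, a named period term is a nearly free improvement. Its value depends on a period shift whose size the documents do not give: negligible up to about 0.25 SD, and substantial from 0.5 SD, given the assumed 80% baseline. Any bias needs unequal completers and is then a small fraction of the shift.

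**What to change.** Section 10.0, Statistical analysis: replace the order-effect sentence with

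> Order effects on safety will be examined by reporting the numbers of discordant participants with the event in period 1 and in period 2, by sequence, with an exact 95% confidence interval for the period-1 share. Non-significance will not be read as absence of an order effect.

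The same display may be used for compliance.

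Section 10.0, SIS and SS-QoL paragraph: add

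> The condition comparison will include crossover period as a fixed effect, with sequence as the design term, and the period estimate will be reported with its confidence interval.

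The cost is wording plus one or two degrees of freedom in the SIS/SS-QoL model (illustrative power 80.4% to 80.2% if there is no shift). No new data or visits are needed. Carry-over, if it is a concern, needs separate comment.

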1.0 Objectives / Specific Aims

- Objectives: To determine the feasibility and safety of using this assistive device, TheraBracelet, every day during waking hours, and to determine if TheraBracelet's instant effects are sustained during prolonged use.
- Design: Community-dwelling chronic stroke survivors will be randomly assigned to either the treatment or control condition for the first month, followed by a 2-week washout period and then crossover to the other condition. In both the treatment and control conditions, participants will be instructed to wear the device for at least 8 hours/day every day during their normal daily activity and come to the laboratory for evaluation prior to and each week of using the device (for a total of 5 evaluations over 4 weeks). The device will deliver vibration (treatment) or no vibration (control). Double-blinding will be possible because the treatment vibration is imperceptible (i.e., subthreshold).
- Primary Aim: Determine the feasibility and safety of using TheraBracelet daily for a month. For feasibility, compliance in using the device will be assessed by weekly self-reports of usage. Hypothesis: TheraBracelet will have a feasibility level comparable to wearing a non-vibrating wristband. To determine safety, participants will be examined at each weekly visit for any worsening of hand sensation, dexterity, grip strength, upper limb pain, spasticity, and wrist skin irritation. Adverse events will be recorded and categorized by severity (minor, moderate, and serious) and device relevance (related to device use or not). Adverse event frequency will be compared between conditions, and with a comparable FDA-approved device, Bioness electrical muscle stimulator. Hypothesis: TheraBracelet will have a safety level equivalent to or better than the comparable FDA-approved assistive device.

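### The feasibility conclusion rests on a yes/no count at 4 h/day; the logged hours are described but have no paired estimate, interval or role in it, so a moderate average loss of wear can pass

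*Combined protocol and SAP*

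**What the plan says.** Section 1.0 states a relative hypothesis: "TheraBracelet will have a feasibility level comparable to wearing a non-vibrating wristband". Section 9.0 tells participants in both conditions to "wear TheraBracelet on the affected wrist every day for at least 8 hours/day during their daily activity over a month", and has them log the times at which they put the device on and take it off each day.

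Section 10.0 defines compliance as "use of the device for at least half the prescribed time" and gives the reason that "4 hours/day is still a substantial use of this assistive device in daily living". The formal plan for the primary aim is to "compare rates of compliance and device-related adverse events between the treatment and control conditions using the test of non-inferiority". The feasibility decision is then stated as a count. Its condition reads "if 3 or less participants out of 24 are incompliant in the treatment vs. control". When that condition is met, the conclusion to be drawn is worded "we will conclude that TheraBracelet is as feasible as wearing a non-vibrating wristband". The next sentence deals with hours: "The cumulative hours of device usage will also be examined for both conditions to inform the general usage trend". No contrast, interval, margin or consequence is given for them.

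**The concern.** The hypothesis compares two conditions, but the criterion that decides it asks only whether each participant-month clears an absolute threshold. Clearing 4 h/day shows useful wear. It does not show that wear was similar with and without vibration. Someone who wears the device 8 h/day in one month and 5 h/day in the other counts as compliant in both.

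The crossover supplies hours from the same person under both conditions, which is the information that a comparability question needs. The plan collects those hours but leaves them outside the conclusion. At stake is a primary-aim statement of equal feasibility that could stand beside logged hours showing a real average drop, with no prespecified estimate to qualify it.

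**Working it through.** **Inputs from the documents.** Prescribed wear is 8 h/day (9.0). The compliance cut is half of that, 0.5 × 8 = 4 h/day (10.0). The rule is 3 or fewer of 24 (10.0). The sample-size inputs are a 20% margin, 10% discordance, 5% significance and 80% power (10.0, power analysis). No SD for wear is given, so every SD below is an assumption shown over a range.

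**1. The plan's own figure.** The sample size of 24 was set for safety, and feasibility borrows its rule. For a paired non-inferiority score test with true difference 0, one-sided 5%:

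n = [(z₀.₉₅√v₀ + z₀.₈₀√v₁)/0.20]², with v₀ = 0.2062 (variance under the null) and v₁ = 0.10

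= [(1.645 × 0.454 + 0.842 × 0.316)/0.20]² = 25.7.

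Exact power of that test at n = 24 is 82.4%. The stated size is reproduced closely and is not in dispute.

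**2. Chance of meeting the count rule after a moderate loss.** Suppose all 24 comply on control, so that the treatment count and the excess over control are the same number. Let treatment wear be normal with mean 6 h/day. Against 8 h/day on control this is a loss of 2 h, or 2/8 = 25%.

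p = Φ((4 − 6)/SD); P(pass) = Σₖ₌₀³ C(24,k) pᵏ(1 − p)²⁴⁻ᵏ

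| SD (h) | (4 − 6)/SD | p | Expected below cut (24p) | P(pass) |
|---|---|---|---|---|
| 1 | −2.00 | 0.023 | 0.55 | 99.8% |
| 1.5 | −1.33 | 0.091 | 2.19 | 82.9% |
| 2 | −1.00 | 0.159 | 3.81 | 45.8% |
| 2.5 | −0.80 | 0.212 | 5.08 | 22.0% |
| 3 | −0.67 | 0.252 | 6.06 | 11.0% |

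For SD 1.5 the terms k = 0 to 3 are 0.101 + 0.243 + 0.280 + 0.206 = 0.829 (from unrounded terms).

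**3. A larger loss.** At exactly 4.5 h/day for everyone, 4.5/8 = 56% of prescribed time, so 0 of 24 fall below the cut and the rule is met. Over 28 days wear would drop from 224 h to 126 h per person, a fall of 98/224 = 44%. With spread around a mean of 4.5 h/day, P(pass) is 45.8% at SD 0.5 h, 3.5% at SD 1 h and 0.3% at SD 2 h.

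**4. What a paired hours estimate would deliver with 24 people.** 90% interval half-width = t₀.₉₅,₂₃ × SD_d/√24 = 1.714 × SD_d/4.899, where SD_d is the SD of the within-person difference.

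| SD_d (h) | Half-width (h/day) |
|---|---|
| 2 | 0.70 |
| 3 | 1.05 |
| 4 | 1.40 |
| 5 | 1.75 |

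The probabilities in steps 2 and 3 are for the count, because the plan ties its conclusion to the count. The non-inferiority test of compliance rates uses the same yes/no variable, and no separate margin is set for it.

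**The case against.** Four points can be made for the plan.

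*Hours are examined.* A reader might infer that feasibility is compared only on the yes/no cut and that a loss on one side of it would go unseen. The documents do not support that. Section 10.0 says hours will be looked at in both conditions, and section 9.0 adds weekly step counts and an acceptance questionnaire. A drop would show in the results. What remains is that nothing prespecified links it to the conclusion.

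*The rule catches large losses.* A reader might infer that a near-halving of wear, from 8 to 4.5 h/day, would be reported as equal feasibility. That happens only if participants hardly differ from one another: at an SD of 1 h the rule is met 3.5% of the time. Moreover, the vibration is imperceptible, the trial is double-blind and the same device is worn in both months, so a uniform fall is remote. This stands. The weakness concerns moderate losses, and it shrinks as spread grows.

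*The cut is a reasoned choice.* Section 10.0 explains why 4 h/day is useful wear. That supports it as an absolute standard and is a good reason to keep it. It does not show similarity to control.

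*A test on hours needs a margin that the plan does not have.* It is tempting to turn the plan's 20% into 1.6 h/day (20% of 8). That 20% is an absolute difference in adverse-event proportions, justified by another device's safety data, so it does not transfer. Power for such a test would be 98%, 92% and 81% at SD_d 2, 2.5 and 3 h, but 70%, 60% and 45% at 3.5, 4 and 5 h. Prescribed wear also has no upper limit: 14 h/day on control and 11 h/day on treatment would fail a 1.6 h margin although everyone exceeded the prescription. This stands against replacing the rule, but not against reporting the paired difference beside it.

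**Conclusion.** The point holds as a limited one. The 4 h/day count can support a statement of adequate use; on its own it does not support equality with the plain wristband. An average loss of 2 h/day would meet the rule with probability 99.8%, 83% or 46% at between-person SDs of 1, 1.5 or 2 h, and 22% or 11% at 2.5 or 3 h. These figures assume full compliance on control, control wear averaging 8 h/day, normally distributed treatment wear and SDs that the documents do not supply. The documents do not support saying that hours are ignored, that a near-halving would usually pass, or that the plan contains a margin for hours.

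**What to change.** In section 10.0, keep the 4 h/day compliance rule as stated. Beside it, prespecify the within-person difference (treatment minus control) in mean logged hours/day with a 90% confidence interval. State how missing log days, participants without second-period hours and a period effect will be handled.

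Word the conclusion from both parts. The rule, with the count given for each condition, supports adequate use in both conditions. Comparable wear is stated only together with the hours difference and its interval. Do not carry the adverse-event 20% over as 1.6 h; if a margin for hours is wanted, the sponsor should justify one before unblinding.

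The cost is analysis wording and slightly more analysis, with no new data, visits or participants. The downside is a less favourable statement if wear drops or the interval is wide. The hours are self-reported, so the interval is only as good as the logs.

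### Repeated measures ANOVA over ten visits, with no missing-data method, can discard participants with any gap; an available-data mixed model with the right error terms would keep them

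*Combined protocol and SAP*

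**What the plan says.** All references are to the combined protocol and SAP.

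- **Method for durability (section 10.0, statistical analysis).** "the hypothesis will be tested using repeated measures ANOVA for each hand function measure". Each of these models is then specified "with factors of vibration (on/off), condition (treatment/control), evaluation time (1-5), and their interactions". Durability is concluded from a significant vibration main effect together with non-significant vibration-by-time and vibration-by-condition interactions.
- **Method for daily living and quality of life (same section).** "Impact of TheraBracelet on activities of daily living and quality of life will be assessed using repeated measures ANOVA for the SIS and SS-QoL". Only the main effect of condition is named; evaluation time is not listed as a factor.
- **Visits (section 9.0, schedule).** "For each condition, participants will come to the laboratory once a week for evaluation for a total of 5 times". Two conditions make ten visits, which agrees with "A follow-up assessment will be administered 4-16 weeks after the 10th session".
- **Sample size (section 10.0, power analysis).** "with the effect size of $f=0.25$ for the Box and Block from our previous study", a correlation of 0.3, 80% power and a 5% level, the plan states that "a sample size of 19 is needed". It aims for data from 24.
- **Allowance for loss.** Sections 5.0 and 10.0 raise recruitment from 24 to 30 for ineligibility after enrollment only. Section 9.0 lets participants leave at any time, and section 11.0 lets the study physician recommend discontinuation after an adverse event. No dropout or missed-visit rate is given.
- **Analysis set.** Intent to treat is named for safety only. No analysis set or missing-data rule is given for the secondary outcomes.

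**The concern.** The durability model has 2 × 2 × 5 = 20 cells per person, filled from ten visits. Standard repeated measures ANOVA needs all 20. A stroke survivor who misses one weekly visit, or leaves after the first month, then contributes nothing to a hand function analysis, even with nine visits of usable data.

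Two things are at stake. The first is power, which matters in an unusual direction here: part of the evidence for durability is the absence of a significant interaction, so a smaller sample makes real desensitization easier to miss. The second is selection. If missed visits or withdrawal relate to tolerance or function, those who complete all ten visits may differ from those randomized.

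**Working it through.** **Inputs from the plan.** f = 0.25, correlation ρ = 0.3, 5% level, required n = 19, target n = 24, ten visits.

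**Assumption.** A per-visit missing rate p, shown from 1% to 10% because the documents give none, with visits missed independently.

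**Step 1: reproduce the 19.** For a within-person F test over m measurements with sphericity, λ = f²·n·m/(1 − ρ), with m − 1 and (n − 1)(m − 1) degrees of freedom. At m = 10 and n = 19, λ = 0.0625 × 19 × 10/0.7 = 16.96 on 9 and 162 df, and power is 0.814. At n = 18 it is 0.786, so 19 is the smallest adequate n. At m = 5 the requirement would be 28, and at m = 20 it would be 13. Of the values tried (2, 3, 4, 5, 8, 10, 20), only m = 10 gives 19. The stated figure therefore appears to assume complete data at all ten visits. With 24 complete participants power is 0.912.

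**Step 2: completers and power.** P(complete) = (1 − p)^10, and expected completers = 24(1 − p)^10. The chance of at least 19 is a binomial tail with n = 24. Average power is the step 1 power averaged over the binomial number of completers. The last column uses 24(1 − p) as a rough effective n for an analysis of all attended visits.

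| p per visit | P(complete) | Expected completers | P(at least 19) | Average power, complete cases | Rough power, all visits |
|---|---|---|---|---|---|
| 1% | 0.904 | 21.7 | 0.98 | 0.87 | 0.91 |
| 2% | 0.817 | 19.6 | 0.73 | 0.82 | 0.91 |
| 3% | 0.737 | 17.7 | 0.37 | 0.77 | 0.90 |
| 5% | 0.599 | 14.4 | 0.04 | 0.65 | 0.89 |
| 10% | 0.349 | 8.4 | <0.01 | 0.37 | 0.87 |

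Expected completers reach 19 at p = 1 − (19/24)^(1/10) = 2.3%. If the first visit cannot be missed, the exponent is 1/9 and the value is 2.6%.

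**Step 3: clustered missingness.** If gaps fall in a few people, what counts is the share of participants with any gap. Six of 24 must be incomplete before 18 remain. If 15% or 20% of participants have a gap, expected completers are 20.4 and 19.2, P(fewer than 19) is 0.14 and 0.34, and average power is 0.84 and 0.81.

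**Step 4: period.** In a participant who starts with treatment, the treatment-minus-control difference contains the condition effect minus the period effect; in the other sequence it contains the sum. With equal sequences the period effect cancels. With, say, 11 and 8 completers, (11 − 8)/19 = 16% of it remains in the condition estimate.

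**Step 5: which random effects a replacement needs.** Suppose a mixed model has random effects for participant and participant-by-period only. Let the residual variance be 1 and the participant-by-vibration variance τ². With complete data on 24 people, the correct mean square for vibration is 1 + 10τ². The pooled residual has 23 × 18 = 414 df and expectation 1 + (23 × 10/414)τ² = 1 + 0.556τ². For τ² = 0.05, 0.10 and 0.20 the ratio of the two is 1.46, 1.89 and 2.70. Dividing 1.96 by its square root gives 1.62, 1.42 and 1.19, hence false-positive rates of about 10%, 15% and 23%. The same test with its own participant-by-vibration error term stays at 5%.

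**The case against.** **The plan never states a complete-case rule.** True. The loss follows from the standard form of the named method. The plan names no alternative, however, so the gap stands.

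**A reader might infer that one missed visit removes a participant from every secondary analysis.** The documents do not support that for SIS and SS-QoL. Only the condition main effect is specified there. If scores are averaged within condition, a single missed visit removes nobody, and only a person with no data in one condition is lost.

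**A reader might infer that falling below 19 makes all the secondary tests underpowered.** The 19 was derived for Box and Block, and it reproduces as an overall test across ten measurements, not as the vibration main effect or its interaction with time. It is the plan's own benchmark, not the power of each test. Power also slopes rather than drops: 0.814 at 19 and 0.786 at 18.

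**The rates are assumed, and independence is the harsher case.** Both stand. At 1% or 2% per visit average power stays above 80%.

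**A reader might infer that the results are biased, or that omitting period confounds the condition effect.** Neither is shown. Nothing in the documents links missed visits to outcome, so selection is a risk only. Section 9.0 balances the sequences, and on and off are tested in random order within a session. In complete balanced data, omitting period costs precision, not validity.

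**Lost power does not only help the durability claim.** The plan also requires a significant vibration main effect, which a smaller sample makes harder to show. The concern is confined to the interaction half of the criterion.

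**Conclusion.** The point holds as a recommended change. The plan names a method that in its standard form needs all ten visits, reserves nothing for dropout, and gives no missing-data approach for the secondary outcomes. Under independent misses the cost on the plan's own calculation is small at 1% to 2% per visit, takes average power slightly below 80% at 3% (0.77), and is material at 5% (0.65). If gaps cluster in up to a fifth of participants, average power remains at or above 0.81. These figures rest on assumed missing rates and on the Box and Block benchmark. The primary feasibility and safety analyses are not affected.

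**What to change.** Replace repeated measures ANOVA for the secondary outcomes with a linear mixed model fitted by REML to all available visits, with small-sample degrees of freedom such as Kenward-Roger.

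- **Hand function, fixed effects:** vibration, condition, evaluation time and their interactions, plus period and sequence.
- **Hand function, random effects:** participant; participant-by-period; participant-by-visit, because on and off share a session; and participant-by-vibration, so that the vibration effect keeps its proper error term. Leaving out the last would undo the gain (step 5).
- **SIS and SS-QoL:** the corresponding model without vibration terms.
- **Also state** the expected missed-visit rate and that the model relies on data missing at random.

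Period and sequence mainly protect precision, and protect balance if loss differs by sequence. They do not correct a bias in complete balanced data.

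The cost is SAP wording and analysis code, a slightly more complex model and a few degrees of freedom. No new data or participants are needed, and the planned hypotheses stay the same.
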